Studies show that breaking up sitting time can reduce cardiometabolic risk markers, thus reducing CVD risk. Within the US National Health and Nutrition Examination Survey (NHANES) study, a detrimental linear association was found between total time spent sitting and waist circumference, high density lipoprotein cholesterol (HDL-C), triglycerides, insulin, insulin sensitivity and β cell function. In addition, independent of total sitting time, a higher number of breaks in sitting per day was significantly beneficially associated with waist circumference, C-reactive protein and fasting plasma glucose. Therefore, both reducing total sitting time and frequently breaking up prolonged periods of sitting are associated with improved cardiometabolic risk in the general population (Healy, et al., 2011).

There is consistent evidence to suggest that breaking up sitting time with 2-5 minutes of light or moderate intensity walking every 20-30 minutes reduces postprandial glucose (Benatti et al., 2015). For example, a randomized cross-over design study conducted by Bailey and Locke (2015) found that breaking up sitting with 2 minutes of light physical activity every 20 minutes reduced postprandial glucose by 16%, but breaking up prolonged sitting with 2 minutes of standing every 20 minutes did not. In participants with impaired metabolic health (e.g. overweight/obese, impaired glycaemia, and people with T2DM), findings have shown

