that breaking up sitting time with both standing and light physical activity have benefits on postprandial cardiometabolic risk markers (including blood pressure, glucose, insulin and triglycerides) (Henson et al., 2016; Dempsey et al., 2016). For instance, a study in dysglycaemic, overweight, postmenopausal women found that breaking up sitting time with 5 minutes of standing every 30 minutes resulted in a 34% reduction in postprandial glucose incremental area under the curve (iAUC). Breaking up sitting with 5 minutes of light-intensity self-paced walking (10-12 on the Borg Rating of Perceived Exertion [RPE] scale) every 30 minutes resulted in a 28% reduction in glucose iAUC. Similar effects were seen for insulin iAUC, which was reduced by 20% with standing breaks and 37% by light intensity walking breaks (Henson, et al., 2016). In patients with T2DM, improvements in postprandial cardiometabolic risk markers (glucose, insulin and triglycerides) were seen when sitting was interrupted with light intensity walking (3 minutes every 30 minutes) and simple resistance exercises (3 minutes every 30 minutes). Overall, there was a reduction in postprandial glucose iAUC of 39% in both conditions and postprandial insulin iAUC by 36% and 37% in the light-intensity walking condition and resistance activities conditions, respectively. Postprandial triglycerides were also significantly attenuated in the simple resistance activities condition, but not in response to light-intensity walking breaks. Light-intensity walking and resistance exercise breaks also resulted in a significant reduction in systolic and diastolic blood pressure (Dempsey, et al., 2016). To our knowledge, there have been no studies conducted to date evaluating the effects of breaking up prolonged sitting on cardiometabolic risk markers in cardiac patients.

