4.1 Objectives

To determine whether breaking up sitting time with standing or light physical activity acutely improves cardiometabolic risk markers and cardiac function in individuals who have suffered a myocardial infarction.

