4.2 Outcome

The primary outcome of this study is postprandial glucose. Other outcome measures include: (i) cardiometabolic risk markers: postprandial triglycerides, high density lipoprotein cholesterol (HDL-C), c-reactive protein, insulin, and blood pressure (ii) cardiac function: global longitudinal strain (%), stroke volume (L) and ejection fraction (%), and (iii) mood and wellbeing.

5 STUDY DESIGN and METHODS of DATA COLLECTION AND DATA ANALYSIS

Study design

A repeated measures, randomised cross over study design will be used. All data collection will take place at the Sport and Exercise Science Laboratories, University of Bedfordshire, [name]. After a preliminary testing session, participants will complete three, 6-hour experimental conditions in a random order: 1) uninterrupted sitting; 2) sitting interrupted with standing breaks, and 3) sitting interrupted with light intensity stepping breaks. There will be a washout period of at least 72 hours between conditions, as previous research suggests that a single session of exercise can affect blood glucose levels for the following 48 hours (Mikines, et al., 1988). Participants will be randomised to order of condition using computer generated random numbers. This will assign them a trial order using block randomization with balanced block sizes. Participants will be blinded to the trial condition until they arrive on the day of their first and second experimental conditions.

Preliminary testing

Patients will first attend a preliminary testing session where they will become accustomed to light intensity stepping on the spot to the beat of a metronome and use of the Borg RPE scale. This will ensure patients are familiar with an intensity that is equivalent to an RPE of 8-11 (very light to light) that will be used in the respective experimental condition. Participants will step to different metronome paces starting at a slow pace and building up gradually every 1-2 minutes until an RPE of 8-11 is found. This imitates the intensity recommended within the warm up of CR, as recommended by BACPR. Height (cm) and weight (kg) will also be measured using a stadiometer (Harpenden 98.602, Holtain Ltd., Crymych) and digital scales

(Tanita BWB0800, Tanita Corp., Tokyo, Japan) respectively, to calculate body mass index (kg/m^2).

Experimental Protocol

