Statistical analyses will be conducted using SPSS Version 23 (IBM, Armonk, NY, USA). Postprandial glucose, insulin, triglycerides, HDL-C, SBP and DBP iAUC will be calculated for each condition using the trapezoidal rule. Mean arterial blood pressure will be calculated as:

$MAP \cong P_{\text{Diastolic blood pressure}} + \frac{1}{3} (P_{\text{systolic blood pressure}} - P_{\text{diastolic blood pressure}})$. Normality of the data will be checked using quantile-quantile plots. Linear mixed models will be used to compare the dependent variables between conditions. Fixed factors for each model will be condition and fasting outcome variable values (as covariates) and participants will be entered as a random factor. Post-hoc analyses will be conducted use the Sidak adjustment if a significant main effect of condition is present. Cohen's d effect sizes will be calculated to describe the magnitude of differences between conditions. Data will be presented as a mean (95% CI). Significance will be set at $p < 0.05$.

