7.2 Sampling

7.2.1 Size of sample

An estimated sample size was calculated using G* Power (version 3.1.9.4). Based on previous data (Bailey, et al., 2019), it was estimated that 18 participants would be needed to detect a medium effect size ($f=0.5$) difference in iAUC postprandial glucose between conditions with 95% power at an alpha level of 5% and within-person correlation of 0.5. To allow for 20% drop out, 23 participants will be recruited. If drop out occurs and recruitment is lower than 18, participants will be replaced to ensure minimum recruitment is met. This decision will be pragmatic in accordance with study timeline.

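### Is the Sidak adjustment after a significant three-condition test an unnecessary second penalty that should be dropped?

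*Protocol*

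**What the plan says.** Under Study design in section 5, "participants will complete three, 6-hour experimental conditions in a random order": uninterrupted sitting, sitting with standing breaks, and sitting with stepping breaks. Three conditions give three pairwise comparisons.

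Under Data analyses in the same section, each outcome is analysed with a linear mixed model. Condition and the fasting value are fixed terms, participant is the random factor, and the significance level is 5%. The pairwise rule is: "Post-hoc analyses will be conducted use the Sidak adjustment if a significant main effect of condition is present". Results are to be presented as means with 95% confidence intervals.

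The objective in section 4.1 is "To determine whether breaking up sitting time with standing or light physical activity acutely improves cardiometabolic risk markers and cardiac function", which only the comparisons with sitting can answer. Section 7.2.1 sizes the trial on the overall difference in glucose iAUC between conditions: "18 participants would be needed to detect a medium effect size", with f = 0.5, 95% power, 5% alpha and a within-person correlation of 0.5. Allowing for 20% dropout, 23 are recruited.

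**The concern.** Two protections are stacked. A pair is tested only if the overall test is significant, and it must then also pass the Sidak level. With three means this is more than family-wise control requires. If any two of the three pairwise equalities hold, the third must hold too, so the only null situations are all three equal or exactly one pair equal. In the first, no false pairwise claim can occur unless the 5% overall test gives a false positive. In the second, only one true null remains, and testing it at 5% is enough. The overall test followed by unadjusted pairwise tests is therefore a closed procedure at 5% per outcome.

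If so, Sidak spends power in a small trial on exactly the comparisons that answer the objective. The standing effect is the uncertain one. Section 1 cites one study in which "breaking up prolonged sitting with 2 minutes of standing every 20 minutes did not" (that is, did not reduce postprandial glucose) and another in which standing breaks lowered glucose iAUC by 34% and walking breaks by 28%. A significant overall result with neither break separated from sitting would be an unhelpful outcome.

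**Working it through.** **Inputs.** Three conditions, 5% alpha and a single participant random factor (section 5); n = 18, f = 0.5 and correlation 0.5 (section 7.2.1). The outcome SD is set to 1 and the fasting covariate is left out. The pattern of means is an assumption, because the protocol gives only f.

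**The plan's own figure.** The noncentrality of the overall F test is n·3·f²/(1 − 0.5). For n = 18 this is 18 × 3 × 0.25/0.5 = 27 on 2 and 34 df, giving power 99.6%. The stated 95% is reached at n = 12, so 18 does not reproduce from the stated inputs. That is a separate matter and makes the trial larger than its stated target needs. The inflation to 23 does reproduce: 18/0.8 = 22.5.

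**Levels.** The Sidak level is 1 − 0.95^(1/3) = 0.01695 per pair. Critical t values on 34 df are 2.511 (Sidak) and 2.032 (unadjusted), a ratio of 1.236, so Sidak intervals are about 1.24 times as wide.

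**Family-wise error** (simulation, overall test first in both):

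| True state | With Sidak | Without Sidak |
|---|---|---|
| All three equal | 4.3% | 5.0% |
| One pair equal, third far away | 1.7% | 5.0% |

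Both rules are valid under the planned model.

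**Power for each break against sitting at f = 0.5.** The standard error of a difference is √(2(1 − 0.5)/18) = 0.236. Each pattern is scaled so that the population SD of the three means is 0.5. In the halfway pattern (0, −0.5, −1) that SD is 0.408, the scale factor is 0.5/0.408 = 1.225, the standing difference is 0.612 and its noncentrality is 0.612/0.236 = 2.6.

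| Pattern | Basis | With Sidak | Without Sidak |
|---|---|---|---|
| Stepping works, standing does not | Section 1 | stepping 97.2% | 99.0% |
| Standing to walking 34:28 | Section 1 | standing 98.8%, stepping 92.6% | 99.5%, 97.2% |
| Both breaks equal | assumed | 97.3% each | 99.1% each |
| Standing halfway to stepping | assumed | standing 54%, stepping 99.5% | 71%, 99.6% |

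Under the two patterns in the background the gain is 0.7 to 4.6 points. At f = 0.5 a significant overall test with neither break separated from sitting occurs in 0.1 to 2.3% of trials with Sidak and 0 to 0.4% without.

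**Half the design effect.** At f = 0.25, which the protocol does not state, the noncentrality is 27/4 = 6.75 and the overall test itself has only about 60% power. Dropping Sidak then gains about 4 to 12 points per break.

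**What the 5% guarantee rests on.** The single participant random factor pools one error variance over all pairs. Suppose the sitting–standing correlation is 0.4 and the other two are 0.6. The variances of the differences are 2(1 − 0.4) = 1.2, 0.8 and 0.8, and the pooled value is their mean, 0.933. The sitting–standing test statistic is then too large by √(1.2/0.933) = 1.134. The critical values act as 2.032/1.134 = 1.79 and 2.511/1.134 = 2.21. Error for a truly equal sitting–standing pair, by simulation, with assumed departures:

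| Departure | With Sidak | Without Sidak |
|---|---|---|
| Correlations 0.4, 0.6, 0.6 | 3.4% | 8.2% |
| Correlations 0.3, 0.6, 0.6 | 4.2% | 9.6% |
| Correlations 0.2, 0.5, 0.5 | 3.8% | 8.9% |
| Stepping SD 30% smaller, correlations 0.5 | 2.6% | 6.9% |

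**The case for a change.** The best case for a change is that it costs one sentence and no participants, that the closed-testing argument is exact under the model the protocol specifies, and that the power of the pairwise comparisons is never stated although the objective depends on them. If standing falls midway between sitting and stepping, the planned rule gives up about 17 points of power for it at the design effect. With all 23 completing, the figures are still about 67% against 82%. The inflated error under unequal correlations comes from a misspecified error term, not from multiplicity, and Sidak is not designed to cure it; for other pairs the same departure lowers the error. The change could also be confined to glucose iAUC.

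The logic and the arithmetic of this case stand. They show that a less strict procedure is available. They do not show that the one chosen is wrong. The halfway pattern matches neither study described in section 1: in one, standing had no effect, and in the other it did slightly better than walking. At f = 0.25 the sample size is the main limit. Sidak's margin under unequal correlation is incidental, but it is real in a trial of 18, and the protocol gives only one planning correlation.

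**Conclusion.** The concern does not hold. The overall test followed by Sidak controls the family-wise error for each outcome under the planned model, and the protocol neither contradicts itself nor claims anything false here. The unused error is 5.0 − 4.3 = 0.7 points when all conditions are equal and 5.0 − 1.7 = 3.3 points when one pair is equal. At the protocol's own effect size and under the patterns its background reports, the cost is about 1 to 5 points of power, from a level that is already 93 to 99%.

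Dropping Sidak is a trade. It would give up simultaneous intervals for the pairwise differences. It would also raise the error for a truly equal pair from 1.7% to 5% on each of the many outcomes in section 4.2, for which the protocol states no adjustment between outcomes, and remove the margin under unequal correlations. Statisticians can reasonably prefer either rule.

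The figures assume complete data on 18 participants, correlation 0.5, no fasting covariate and the stated patterns of means. With a fasting covariate in the model, the error rates without Sidak stayed near 5% (5.1% and 4.8%). The conclusion would be open to review if the sponsor had reason to expect a standing effect about midway to stepping.

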6 STUDY SETTING

All testing will take place at the University of Bedfordshire Sport and Exercise Science Laboratories.

7 SAMPLE AND RECRUITMENT

7.1 Eligibility Criteria

7.1.1 Inclusion criteria

- Patients post myocardial infarction (ST wave elevated MI or Non-ST wave elevated MI) within the past three months (confirmed by elevated blood biomarkers or electrocardiographic changes), in which the procedure/ recovery uncomplicated and are therefore classified as low risk.
- Aged 40 years or above.
- Any ethnicity.
- Individuals with diet controlled type 2 diabetes mellitus

7.1.2 Exclusion criteria

- Previous MI
- Under 40 years of age.
- Unable to provide valid informed consent (lack of mental capacity).
- Not had a cardiac event diagnosed within the past three months.
- Existing comorbidities including cancer, chronic kidney disease and gastro-oesophageal diseases.
- Unstable coronary disease.
- Diagnosed diabetes and use of medication.
- Disease or conditions with a prognosis of less than 6 months to end of life (palliative care). Any known blood borne disease.
- Unable to stand and engage in light-intensity stepping.

7.2 Sampling

7.2.1 Size of sample

An estimated sample size was calculated using G* Power (version 3.1.9.4). Based on previous data (Bailey, et al., 2019), it was estimated that 18 participants would be needed to detect a medium effect size ($f=0.5$) difference in iAUC postprandial glucose between conditions with 95% power at an alpha level of 5% and within-person correlation of 0.5. To allow for 20% drop out, 23 participants will be recruited. If drop out occurs and recruitment is lower than 18, participants will be replaced to ensure minimum recruitment is met. This decision will be pragmatic in accordance with study timeline.

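### The sample-size paragraph calls f = 0.5 a medium effect, but 18 participants have only about 60% power for a conventional medium effect, and 18 does not follow from the printed inputs

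*Protocol*

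**What the plan says.** The whole justification for the sample size is in Protocol section 7.2.1. It reports a G*Power calculation based on earlier data and concludes that "18 participants would be needed to detect a medium effect size ($f=0.5$) difference in iAUC postprandial glucose between conditions with 95% power". The significance level is set at 0.05, and the correlation between a participant's conditions is taken as 0.5. Recruitment is then inflated: "To allow for 20% drop out, 23 participants will be recruited". The paragraph does not print the test family, the number of repeated measurements or a nonsphericity correction (epsilon).

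The design behind the calculation is in other sections. In section 5 (Study design), "participants will complete three, 6-hour experimental conditions in a random order". In section 4.2, "The primary outcome of this study is postprandial glucose". In section 5 (Data analyses), "Linear mixed models will be used to compare the dependent variables between conditions", with the fasting value of each outcome as a covariate and Sidak-adjusted post-hoc comparisons.

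**The concern.** There are two separate problems in one sentence.

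1. **The label and the number disagree.** By the usual convention for Cohen's f (0.10 small, 0.25 medium, 0.40 large), 0.5 is larger than large. The protocol defines no other benchmark. The sentence therefore names two different effects as the one powered at 95%.
2. **The stated number does not reproduce.** The printed f, alpha, power and correlation, applied to three conditions, do not give 18 unless some further setting is added.

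The first matters more. A reader who relies on the word would believe that a medium effect on the primary outcome has only a 5% chance of being missed, and could read a null result as near-certain evidence against such an effect.

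**Working it through.** **Inputs.** From section 7.2.1: f = 0.5, alpha = 0.05, power 95%, correlation ρ = 0.5, N = 18, drop-out 20%. From section 5: m = 3 conditions, one group. Epsilon (ε) is not given; with three conditions it lies between 0.5 and 1, so that range is shown. The protocol sets no value for a medium effect; f = 0.25 is the usual convention and is an assumption here.

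**Formula** (repeated-measures F test, within factor, noncentral F):

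- λ = ε · f² · N · m / (1 − ρ)
- df1 = ε(m − 1), df2 = ε(N − 1)(m − 1)
- power = P(noncentral F with df1, df2, λ exceeds the 95th percentile of the central F)

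**Step 1: the protocol's own figure (f = 0.5, ε = 1).**

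- N = 11: λ = 0.25 × 11 × 3 / 0.5 = 16.5, df 2 and 20, power 93.0%.
- N = 12: λ = 18.0, df 2 and 22, power 95.2%. The required N is 12.
- N = 18: λ = 27.0, df 2 and 34, critical F 3.28, power 99.6%.

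The drop-out step does reproduce: 18 / 0.8 = 22.5, rounded up to 23. The discrepancy is therefore in the base calculation.

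**Step 2: what would give 18.** Examples, not a complete list:

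- ε = 0.6, f = 0.5, ρ = 0.5: λ = 0.6 × 27.0 = 16.2, power 96.1%.
- ε = 1, f = 0.40, ρ = 0.5: λ = 0.16 × 18 × 3 / 0.5 = 17.28, power 95.4% (N = 17 gives 94.1%).
- ε = 0.75, ρ = 0.4, f = 0.5: power 96.1%.

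Each needs a value that is unstated or that differs from the printed one.

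**Step 3: power for a medium effect (f = 0.25, ρ = 0.5).** At N = 18 and ε = 1, λ = 0.0625 × 18 × 3 / 0.5 = 6.75, and power is 59.7%.

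| ε | N needed, f = 0.5 | Power, f = 0.5, N = 18 | Power, f = 0.25, N = 18 | Power, f = 0.25, N = 23 | Smallest f, N = 18, 95% power | Smallest f, N = 18, 80% power |
|---|---|---|---|---|---|---|
| 1 | 12 | 99.6% | 59.7% | 72.1% | 0.396 | 0.312 |
| 0.8 | 14 | 98.7% | 53.0% | 64.9% | 0.432 | 0.339 |
| 0.6 | 18 | 96.1% | 45.3% | 56.1% | 0.484 | 0.378 |
| 0.5 | 20 | 93.3% | 41.1% | 51.0% | 0.521 | 0.405 |

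The N = 23 column assumes no drop-out. Power at f = 0.25 is highest at ε = 1, so no choice of ε brings it near 95%. For scale, 95% power at f = 0.25 needs 43 completers at ε = 1. A simulation of 100,000 trials (compound symmetry, repeated-measures ANOVA) agrees: 0.996 at f = 0.5 and 0.595 at f = 0.25 with N = 18, and 0.952 at f = 0.5 with N = 12.

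**Step 4: could the correlation or the covariate rescue the claim?** At f = 0.25, N = 18 and ε = 1, power is 70% at ρ = 0.6, 83% at 0.7 and 95% at 0.8, against a stated 0.5. Adjusting for the fasting value acts in the same way as lowering 1 − ρ. For 95% power, 1 − ρ must fall from 0.5 to 0.200 at ε = 1, a reduction of 1 − 0.200/0.5 = 60%. At ε = 0.6 it must fall to 0.133, a reduction of 73%. The protocol gives no figure for how much the covariate removes.

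**The case against.** The strongest reply is that the target is printed as a number. A reader sees f = 0.5 beside the word, the protocol never claims power at f = 0.25, and the scale for medium is a convention from outside the document. At f = 0.5 the claim of 95% is met or exceeded for any ε from about 0.56 to 1. All of this stands, and it means that the trial is not shown to be underpowered for the effect it prints. It does not remove the contradiction: the word describes the effect that the primary analysis is said to detect, and under the only common scale it names a different effect.

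On the second problem, 18 can be reached by a route that uses the Sidak adjustment planned in section 5. Suppose both break conditions differ equally from uninterrupted sitting. The spread of the three means is then √2/3 of that difference, so f = 0.5 implies a difference of 0.5 × 3/√2 = 1.06 standard deviations. At ρ = 0.5 the SD of a paired difference equals the outcome SD, so 1.06 is also the paired effect size. A paired t test at the Sidak level 1 − 0.95^(1/3) = 0.01695 then has 95.7% power at 18 and 94.3% at 17. That is correct, but it needs an assumed pattern of means and a test that the sample-size paragraph does not mention. It is one more unstated setting that gives 18. What stands is that this part concerns a calculation that cannot be reproduced as reported, in a conservative direction, and not a shortfall.

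It is also fair that the F test omits the fasting covariate, so the 60% and 45% figures are for an unadjusted analysis. Step 4 of the working shows how much the covariate would have to remove. Finally, the planned 95% confidence intervals and Cohen's d will show what a null result excludes, whatever the advance statement says.

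**Conclusion.** The concern holds. As written, the power statement for the primary outcome attaches 95% power to a medium effect, while its number is above the conventional value for large. If the word is taken at face value, the chance of missing such an effect with 18 completers is about 40% at ε = 1 and about 55% at ε = 0.6, not 5%. If the number is taken at face value, the printed inputs need 12 at ε = 1, and 18 gives 99.6% power.

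This rests on the usual convention for f, three conditions, the stated correlation of 0.5, a repeated-measures F test in place of the planned mixed model, and ε assumed over its range because none is given. The defect is in the advance statement of power. It should be corrected, but it gives no reason to change the number of participants.

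**What to change.** Keep 18 completers and 23 recruited. In section 7.2.1:

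- Delete the word medium, or call f = 0.5 large.
- Check the saved G*Power run and state the f, correlation, number of measurements and ε that were entered, with the power they give at 18. If the run used f near 0.40 and not 0.5, correct the printed value.
- Add one sentence, for example: *For a medium effect (f = 0.25, correlation 0.5), 18 participants give about 60% power if epsilon is 1 and about 45% if epsilon is 0.6, before any gain from adjusting for fasting values.*

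The cost is one paragraph of wording and a look at the saved run. Sample size, conduct and analysis do not change. The only drawback is that the stated power for a medium effect becomes less favourable.
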